4. OBJECTIVES AND ENDPOINTS

| Objectives | Endpoints |
|--|--|
| Primary | |
| 
 To evaluate the safety and tolerability after single IV dosing of GSK2831781 in healthy Japanese and Caucasian participants, and SC dosing in healthy Caucasian participants | 
 AEs, vital signs, clinical laboratory values (haematology, clinical chemistry, and urinalysis), 12-lead ECG Local tolerability |
| Secondary | |
| 
 To evaluate the PK of GSK2831781 after a single IV dose in healthy Japanese and Caucasian participants (Part A) | 
 GSK2831781 PK parameters following single IV dose: area under the plasma concentration-time curve [AUC(0-t)], maximum observed plasma concentration (C_{max}), time of occurrence of C_{max} (t_{max}) |
| 
 To evaluate the PK of GSK2831781 after a single SC dose in healthy Caucasian participants (Part B) | 
 GSK2831781 PK parameters following single SC dose: AUC(0-t), C_{max}, t_{max}, bioavailability (F) |
| 
 To evaluate the effect of a single IV or SC dose of GSK2831781 on depletion of LAG3+ T cells in blood | 
 PK/PD relationship between plasma PK of GSK2831781 and LAG3+ T cells in blood over time |
| 
 To investigate the immunogenicity of single IV and SC doses of GSK2831781 | 
 ADAs over time |
| Exploratory | |
| 
 To evaluate the concentration-time profiles of GSK2831781 after a single IV dose in healthy Japanese and Caucasian participants (Part A) | 
 GSK2831781 PK concentrations over time following single IV dose |
| 
 To evaluate the concentration-time profiles of GSK2831781 after a single | 
 GSK2831781 PK concentrations over time following single SC dose |

| Objectives | Endpoints |
|---|--|
| SC dose in healthy Caucasian participants (Part B) | |
| 
 To evaluate the effect of a single IV or SC dose of GSK2831781 on soluble LAG3 (sLAG3) concentrations | 
 Soluble LAG3 (sLAG3) concentrations in blood over time |

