10.4.1. Safety Analyses

All safety analyses will be performed on the Safety Population.

| Endpoint | Statistical Analysis Methods |
|----------|---|
| Primary | The primary safety analyses will be based on the "Safety" population. These endpoints will be presented in tabular and/or graphical format and summarised descriptively according to GSK's Integrated Data Standards Library standards. |

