11.2. Appendix 2: Clinical Laboratory Tests

- The tests detailed in [Table 1](#) will be performed by the local laboratory.
- Protocol-specific requirements for inclusion or exclusion of participants are detailed in [Section 6](#) of the protocol.
- Additional tests may be performed at any time during the study as determined necessary by the investigator or required by local regulations.

Table 1 Protocol-Required Safety Laboratory Assessments

| Laboratory Assessments | Parameters | | | |
|---------------------------------|---|---|---|---|
| Haematology | Platelet Count | RBC Indices: Mean Corpuscular Volume (MCV) Mean Corpuscular Haemoglobin (MCH) %Reticulocytes | | White Blood Cell (WBC) count with Differential: Neutrophils Lymphocytes Monocytes Eosinophils Basophils |
| | Red Blood Cell (RBC) Count | | | |
| | Haemoglobin | | | |
| | Haematocrit | | | |
| Clinical Chemistry ¹ | Blood Urea Nitrogen (BUN) | Potassium | Aspartate Aminotransferase (AST)/Serum Glutamic-Oxaloacetic Transaminase (SGOT) | Total and direct bilirubin |
| | Creatinine Estimated Glomerular Filtration Rate (eGFR) | Sodium | Alanine Aminotransferase (ALT)/Serum Glutamic-Pyruvic Transaminase (SGPT) | Total Protein |
| | Glucose [non-fasting] | Calcium | Alkaline phosphatase | |
| Routine Urinalysis | 
 • Specific gravity • pH, glucose, protein, blood, ketones, bilirubin, urobilinogen, nitrite, leukocyte esterase by dipstick • Microscopic examination (if blood or protein is abnormal) | | | |
| Other Screening Tests | 
 • Breath alcohol screen • Urine drug screen (to include at minimum: amphetamines, barbiturates, cocaine, opiates, cannabinoids and benzodiazepines) • Serology: HIV antibody, HbsAg, HbcAb, HCV antibody, EBV antibody³, CMV antibody³, VZV antibody³ • Quantiferon test for TB | | | |

NOTES :

1. Details of liver chemistry stopping criteria and required actions and follow-up assessments after liver stopping or monitoring event are given in Section 8.2.3. All events of ALT $\geq 3 \times$ upper limit of normal (ULN) and bilirubin $\geq 2 \times$ ULN (>35% direct bilirubin) or ALT $\geq 3 \times$ ULN and international normalized ratio (INR) >1.5, if INR measured, which may indicate severe liver injury (possible Hy's Law), must be reported as an SAE (excluding studies of hepatic impairment or cirrhosis).

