15.8.4. Urinalysis

Urinalysis			
Test Analyte	Units	Category	Clinical Concern Range
Bilirubin		High	>1+
Glucose		High	>1+
Ketone		High	>2+
Leukocytes (dipstick)		High	>1+
Nitrite		High	Positive
Occult blood (dipstick)		High	>1+
pH		Low	<4.6
		High	>8
Protein		High	>1+
RBC (microscopy)	cells/hpf	High	>3
Specific gravity		Low	<1.001
		High	>1.035
Urobilinogen	mg/dL	High	>1
WBC (microscopy)	cells/hpf	High	>5

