15.12.5. Safety Tables**Part A**

Safety Tables (Part A)					
No.	Population	IDSL / Example Shell	Title	Programming Notes	Deliverable [Priority]
Adverse Events (AEs)					
2.1.	Safety	AE1	Part A: Summary of All Adverse Events by System Organ Class and Preferred Term	IA: By geographic ancestry. SAC: By treatment and geographic ancestry.	IA SAC
2.2.	Safety	AE3	Part A: Summary of Drug-Related Adverse Events	IA: By geographic ancestry. SAC: By treatment and geographic ancestry.	IA SAC
2.3.	Safety	AE3	Part A: Summary of Non-Serious Drug-Related Adverse Events by Overall Frequency	By treatment and geographic ancestry.	SAC
2.4.	Safety	AE5A	Part A: Summary of All Adverse Events by Maximum Intensity by System Organ Class and Preferred Term	Page by treatment and geographic ancestry.	SAC
2.5.	Safety	AE5A	Part A: Summary of Drug-Related Adverse Events by Maximum Intensity by System Organ Class and Preferred Term	Page by treatment and geographic ancestry.	SAC
Serious and Other Significant Adverse Events					
2.6.	Safety	AE16	Part A: Summary of Serious Adverse Events by System Organ Class and Preferred Term (Number of Subjects and Occurrences)	IA: By geographic ancestry. SAC: By treatment and geographic ancestry.	IA SAC
2.7.	Safety	AE3	Part A: Summary of Serious Drug-Related Adverse Events by Overall Frequency	IA: By geographic ancestry. SAC: By treatment and geographic ancestry.	IA SAC
2.8.	Safety	AE3	Part A: Summary of Adverse Events Leading to Permanent Discontinuation of Study Treatment or Withdrawal from Study	By treatment and geographic ancestry.	SAC

Safety Tables (Part A)					
No.	Population	IDSL / Example Shell	Title	Programming Notes	Deliverable [Priority]
Laboratory: Chemistry					
2.9.	Safety	LB1	Part A: Summary of Chemistry Changes from Baseline	By treatment and geographic ancestry.	SAC
Laboratory: Haematology					
2.10.	Safety	LB1	Part A: Summary of Haematology Changes from Baseline	By treatment and geographic ancestry. IA: Only include the following parameters: Neutrophils, Lymphocytes.	IA SAC
Laboratory: Urinalysis					
2.11.	Safety	LB1	Part A: Summary of Urine Concentration Changes from Baseline	By treatment and geographic ancestry.	SAC
Laboratory: Hepatobiliary (Liver)					
2.12.	Safety	LIVER1	Part A: Summary of Liver Monitoring/Stopping Event Reporting	By treatment and geographic ancestry.	IA SAC
2.13.	Safety	LIVER10	Part A: Summary of Hepatobiliary Laboratory Abnormalities	By treatment and geographic ancestry.	SAC
ECG					

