2.14.	Safety	EG1	Part A: Summary of ECG Findings	By treatment and geographic ancestry.	SAC
2.15.	Safety	EG10	Part A: Summary of Maximum QTc Values Post-Baseline Relative to Baseline by Category	By treatment and geographic ancestry.	SAC
2.16.	Safety	EG2	Part A: Summary of Change from Baseline in ECG Values by Visit	By treatment and geographic ancestry.	SAC
Vital Signs					
2.17.	Safety	VS1	Part A: Summary of Change from Baseline in Vital Signs	By treatment and geographic ancestry.	SAC

Part B

Safety Tables (Part B)					
No.	Population	IDSL / Example Shell	Title	Programming Notes	Deliverable [Priority]
Adverse Events (AEs)					
2.18.	Safety	AE1	Part B: Summary of All Adverse Events by System Organ Class and Preferred Term	By treatment.	SAC
2.19.	Safety	AE3	Part B: Summary of Drug-Related Adverse Events	By treatment.	SAC
2.20.	Safety	AE3	Part B: Summary of Non-Serious Drug-Related Adverse Events by Overall Frequency	By treatment.	SAC
2.21.	Safety	AE5A	Part B: Summary of All Adverse Events by Maximum Intensity by System Organ Class and Preferred Term	Page by treatment.	SAC
2.22.	Safety	AE5A	Part B: Summary of Drug-Related Adverse Events by Maximum Intensity by System Organ Class and Preferred Term	Page by treatment.	SAC
Serious and Other Significant Adverse Events					
2.23.	Safety	AE16	Part B: Summary of Serious Adverse Events by System Organ Class and Preferred Term (Number of Subjects and Occurrences)	By treatment.	SAC
2.24.	Safety	AE3	Part B: Summary of Serious Drug-Related Adverse Events by Overall Frequency	By treatment.	SAC
2.25.	Safety	AE3	Part B: Summary of Adverse Events Leading to Permanent Discontinuation of Study Treatment or Withdrawal from Study	By treatment.	SAC
Laboratory: Chemistry					
2.26.	Safety	LB1	Part B: Summary of Chemistry Changes from Baseline	By treatment.	SAC
Laboratory: Haematology					
2.27.	Safety	LB1	Part B: Summary of Haematology Changes from Baseline	By treatment.	SAC

Safety Tables (Part B)					
No.	Population	IDSL / Example Shell	Title	Programming Notes	Deliverable [Priority]
Laboratory: Urinalysis					
2.28.	Safety	LB1	Part B: Summary of Urine Concentration Changes from Baseline	By treatment.	SAC
Laboratory: Hepatobiliary (Liver)					
2.29.	Safety	LIVER1	Part B: Summary of Liver Monitoring/Stopping Event Reporting	By treatment.	SAC
2.30.	Safety	LIVER10	Part B: Summary of Hepatobiliary Laboratory Abnormalities	By treatment.	SAC
ECG					
2.31.	Safety	EG1	Part B: Summary of ECG Findings	By treatment.	SAC

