24.	Safety	LIVER7	Part A: Listing of Liver Biopsy Details		SAC

ICH Listings (Part A)					
No.	Population	IDSL / Example Shell	Title	Programming Notes	Deliverable [Priority]
25.	Safety	LIVER8	Part A: Listing of Liver Imaging Details		SAC
All Laboratory					
26.	Safety	LB5	Part A: Listing of All Laboratory Data for Subjects with Any Value of Potential Clinical Importance		SAC
27.	Safety	LB5	Part A: Listing of Laboratory Values of Potential Clinical Importance		SAC
28.	Safety	LB14	Part A: Listing of Laboratory Data with Character Results	IA: Only include the following parameters: Neutrophils, Lymphocytes	IA SAC
29.	Safety	UR2A	Part A: Listing of Urinalysis Data for Subjects with Any Value of Potential Clinical Importance		SAC
ECG					
30.	Safety	EG3	Part A: Listing of All ECG Values for Subjects with Any Value of Potential Clinical Importance		SAC
31.	Safety	EG3	Part A: Listing of ECG Values of Potential Clinical Importance		SAC
32.	Safety	EG5	Part A: Listing of All ECG Findings for Subjects with an Abnormal ECG Finding		SAC
Vital Signs					
33.	Safety	VS4	Part A: Listing of All Vital Signs for Subjects with any Value of Potential Clinical Importance		SAC

Part B

ICH Listings (Part B)					
No.	Population	IDSL / Example Shell	Title	Programming Notes	Deliverable [Priority]
Subject Disposition					
34.	Safety	ES2	Part B: Listing of Reasons for Study Withdrawal		SAC
35.	Screened	ES7	Part B: Listing of Reasons for Screen Failure		SAC
36.	Safety	SD2	Part B: Listing of Reasons for Study Treatment Discontinuation		SAC
37.	Safety	BL1	Part B: Listing of Subjects for Whom the Treatment Blind was Broken		SAC
38.	Safety	TA1	Part B: Listing of Planned and Actual Treatments		SAC
Protocol Deviations					
39.	Safety	DV2	Part B: Listing of Important Protocol Deviations		SAC
40.	Safety	IE3	Part B: Listing of Subjects with Inclusion/Exclusion Criteria Deviations		SAC
Populations Analysed					
41.	Screened	SP3	Part B: Listing of Subjects Excluded from Any Population		SAC
Demographic and Baseline Characteristics					
42.	Safety	DM2	Part B: Listing of Demographic Characteristics		SAC
43.	Safety	DM9	Part B: Listing of Race		SAC
Medical Conditions and Prior/Concomitant Medications					
44.	Safety	MH2	Part B: Listing of Current/Past Medical Conditions		SAC
45.	Safety	CM2	Part B: Listing of Concomitant Medications		SAC
Exposure and Treatment Compliance					
46.	Safety	EX3	Part B: Listing of Exposure Data		SAC

ICH Listings (Part B)					

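### The planned urinalysis tables do not fit seven of the ten routine parameters, so dipstick changes not recorded as adverse events have no stated summary by arm

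*SAP*

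**What the plan says.** The primary endpoint in protocol section 4 is "AEs, vital signs, clinical laboratory values (haematology, clinical chemistry, and urinalysis), 12-lead ECG", plus local tolerability. On reporting, protocol 10.4.1 says: "These endpoints will be presented in tabular and/or graphical format and summarised descriptively", following the sponsor's display standards.

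The dipstick part of the panel in protocol Appendix 2 is "pH, glucose, protein, blood, ketones, bilirubin, urobilinogen, nitrite, leukocyte esterase by dipstick". Specific gravity is listed separately, and microscopy is done only when blood or protein is abnormal.

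SAP 8.2 says that laboratory summaries cover all post-baseline assessments, and refers the reader to Appendix 12 for the displays. Under urinalysis, Appendix 12 plans Table 2.11, "Part A: Summary of Urine Concentration Changes from Baseline", and Table 2.28, "Part B: Summary of Urine Concentration Changes from Baseline". Both are on shell LB1 and both are for the final analysis only. The urinalysis listing for Part A is Listing 29, "Part A: Listing of Urinalysis Data for Subjects with Any Value of Potential Clinical Importance". Listing 62 is its Part B equivalent. Listings 28 and 61 hold laboratory results recorded as characters.

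**The concern.** A change from baseline needs a numeric result. Most of the urinalysis panel appears to be recorded as grades or as positive/negative, so the one display named for it does not suit most of what it is meant to summarise. Neither SAP Table 1, which records departures from the protocol's analysis, nor any other section says that the graded results are deliberately left out.

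At stake is a by-arm count for a named component of the primary endpoint. Protocol 5.6 says the placebo arms are there so that events attributable to treatment can be told apart from those that are not. For dipstick results below the investigator's threshold of clinical significance, the plan states no table in which that comparison can be read.

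**Working it through.** No sample-size or power figure is involved. The check matches parameters to result scales, and then to displays.

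**1. Size of the panel.** Protocol Appendix 2 gives specific gravity plus nine dipstick items: 1 + 9 = 10 routine parameters. The schedules of activities collect them at nine post-dose visits in each part (Part A: 24 h and Days 3, 8, 15, 29, 43, 57, 85, 112; Part B: Days 2, 3, 8, 15, 29, 43, 57, 85, 112).

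**2. Result scale, from the limits in SAP 15.8.4.**

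| Scale of the limit | Parameters | Count |
|---|---|---|
| Numeric | specific gravity, pH, urobilinogen (mg/dL) | 3 |
| Grade, no unit (>1+ or >2+) | protein, blood, glucose, ketones, bilirubin, leukocytes | 6 |
| Positive, no unit | nitrite | 1 |

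So 6 + 1 = 7 of 10 have no numeric limit. Red and white cell counts on microscopy also have numeric limits (cells/hpf), but they are conditional tests outside the ten.

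**3. Is there a scoring rule?** The only character-to-number rule is in SAP 15.6.3. It covers results reported as below or above a limit, for tests expected to be numeric. It assigns no score to negative, 1+ or 2+.

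**4. Displays available.** SAP 15.12.1 numbers the safety tables 2.1 to 2.34, and the list contains 17 for Part A and 17 for Part B: 17 + 17 = 34. Two of the 34 (2.11 and 2.28) are urinalysis, both change from baseline. None is a frequency, shift or potential-clinical-importance table for urinalysis. Both safety figures are haematology. SAP 15.6.1 refers to summary tables of values of potential clinical importance, but Appendix 12 contains none for laboratory data.

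**5. Where a graded result can appear.**
- If the investigator judges it clinically significant, it is an adverse event (protocol 9.1.4 and 11.3.1). It is then counted by treatment and ancestry in Tables 2.1 and 2.4, and by treatment in 2.18 and 2.21.
- Otherwise it can appear as a row in Listing 28 or 61.
- It can also appear in Listing 29 or 62 if the participant has any urinalysis value past its limit. The limit for protein and blood is >1+, so a 1+ result does not pass it by itself.

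Only the first route gives a count by arm.

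**6. Comparison within the same list.** At the same sample sizes, Appendix 12 plans tables of hepatobiliary laboratory abnormalities (2.13, 2.30), ECG findings (2.14, 2.31) and QTc by category (2.15, 2.32).

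**The case against.** The strongest reply is that LB1 has not been seen. It is a standard shell, SAP Appendix 13 makes mock shells available only on request, and SAP 8.2 places urinalysis under the sponsor's core standards. SAP 15.5.2 gives frequency and percent as the convention for categorical data, so LB1 might show graded results that way. This stands as a limit on the point. That LB1 is numeric is an inference from the table titles and from its use for chemistry and haematology. The general reference to standards does not settle the matter, because SAP 8.2 points to Appendix 12 for the planned displays and no table there is identified as doing this.

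A reader might infer more than the documents support, in three ways.

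- *That graded results get no summary of any kind, so affected participants cannot be counted by arm.* Clinically significant changes are counted by arm as adverse events. At the final analysis Listings 28 and 61 carry no clinical-importance restriction, so with 16 and 20 planned participants a reader could also count by hand.
- *That new 1+ protein or blood can never bring a participant into Listing 29 or 62.* If 1+ counts as abnormal it prompts microscopy, and a red cell count above 3 or a white cell count above 5 cells/hpf would trigger the listing.
- *That proteinuria or haematuria is a documented risk of the drug.* The immune-complex changes in protocol 3.3.1 come from one monkey and were transient and minimal. No urinary or renal finding is named, and the same section says animal immunogenicity does not predict the human response. The risk table lists no renal risk.

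It is also fair to say that small groups limit what any table can show, since Part A placebo has 2 participants per ancestry group. But the plan tabulates ECG and liver categories at these sizes, so size alone does not explain the omission.

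**Conclusion.** The point holds in a limited form. The display named for urinalysis does not suit 7 of the 10 routine parameters, and the plan states no other by-arm summary for graded changes that fall short of clinical significance. This is more than missing detail, because the named table and most of the data do not match. It is still modest in weight: the results are listed, the significant ones are counted as adverse events, and the study tests no hypotheses.

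The conclusion rests on two assumptions: that LB1 is a numeric change-from-baseline layout, and that the seven parameters are recorded on the scale of their limits in SAP 15.8.4. If the sponsor can show that LB1 or another listed display already gives grade counts by arm, one sentence in Appendix 12 saying so would close the point.

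**What to change.** Limit Tables 2.11 and 2.28 to the numeric parameters: specific gravity, pH, and urobilinogen if it is reported as a number. Add one categorical table per part giving, for each dipstick parameter, n (%) by baseline grade against worst post-baseline grade. Part A should be shown by treatment (planned 12 active, 4 placebo) and by treatment within ancestry (6, 6, 2, 2). Part B should be shown by treatment (8, 8, 4). A grade-by-visit breakdown is not needed. State whether the worst grade is taken over scheduled visits only, since SAP 15.5.2 keeps unscheduled visits out of summary tables. Update the table numbering in SAP 15.12.1.

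The cost is two extra tables from data already collected, with no change to trial conduct. The downside is sparse cells, with 2 to 12 participants per column, so the tables are descriptive only.

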15.12.6. Safety Figures**Part A**

Pharmacokinetic Tables (Part A)					
No.	Population	IDSL / Example Shell	Title	Programming Notes	Deliverable [Priority]
Laboratory: Haematology					
2.1.	Safety	[Non-standard] SAFE_F1	Part A: Individual Plots of Haematology	By treatment and geographic ancestry. Only include the following parameters: Neutrophils, Lymphocytes.	IA
2.2.	Safety	[Non-standard] SAFE_F2	Part A: Mean (\pm SD) Plots of Haematology	By treatment and geographic ancestry. Only include the following parameters: Neutrophils, Lymphocytes.	IA

15.12.7. Pharmacokinetic Tables**Part A**

Pharmacokinetic Tables (Part A)					
No.	Population	IDSL / Example Shell	Title	Programming Notes	Deliverable [Priority]
Pharmacokinetic Concentrations					
3.1.	PK	PK01	Part A: Summary of GSK2831781 Plasma Pharmacokinetic Concentration-Time Data	Include 95% Confidence Interval for the mean. By treatment and geographic ancestry. IA: only include data up to Day 29.	IA SAC
Pharmacokinetic Parameters					
3.2.	PK	PK03	Part A: Summary of Derived GSK2831781 Plasma Pharmacokinetic Parameters	Include 95% Confidence Interval for the mean. By treatment and geographic ancestry.	IA SAC
3.3.	PK	PK05	Part A: Summary of Log-Transformed Derived GSK2831781 Plasma Pharmacokinetic Parameters	By treatment and geographic ancestry.	IA SAC
Pharmacokinetic Statistical Analyses					
3.4.	PK	[Non-standard] PK_T1	Part A: Table of Ethnosensitivity Model Results		SAC

Part B

Pharmacokinetic Tables (Part B)					
No.	Population	IDSL / Example Shell	Title	Programming Notes	Deliverable [Priority]
Pharmacokinetic Concentrations					
3.5.	PK	PK01	Part B: Summary of GSK2831781 Plasma Pharmacokinetic Concentration-Time Data	Include 95% Confidence Interval for the mean. By treatment.	SAC
Pharmacokinetic Parameters					
3.6.	PK	PK03	Part B: Summary of Derived GSK2831781 Plasma Pharmacokinetic Parameters	Include 95% Confidence Interval for the mean. By treatment.	SAC
3.7.	PK	PK05	Part B: Summary of Log-Transformed Derived GSK2831781 Plasma Pharmacokinetic Parameters	By treatment.	SAC
Pharmacokinetic Statistical Analyses					
3.8.	PK	[Non-standard] PK_T1	Part B: Table of Bioavailability Model Results		SAC

15.12.8. Pharmacokinetic Figures

Part A

Pharmacokinetic Figures (Part A)					
No.	Population	IDSL / Example Shell	Title	Programming Notes	Deliverable [Priority]
Pharmacokinetic Concentrations					
3.1.	PK	PK24	Part A: Individual GSK2831781 Plasma Concentration-Time Plots (Linear and Semi-log) by Treatment and Geographic Ancestry	By treatment and geographic ancestry. IA: do not show subject IDs. Different colours and symbols for treatment and geographic ancestry. IA: only include data up to Day 29.	IA SAC
3.2.	PK	PK19	Part A: Mean (\pm SD) GSK2831781 Plasma Concentration-Time Plots (Linear and Semi-log) by Treatment and Geographic Ancestry	By treatment and geographic ancestry. IA: only include data up to Day 29.	IA SAC

Part B

Pharmacokinetic Figures (Part B)					
No.	Population	IDSL / Example Shell	Title	Programming Notes	Deliverable [Priority]
Pharmacokinetic Concentrations					
3.3.	PK	PK24	Part B: Individual GSK2831781 Plasma Concentration-Time Plots (Linear and Semi-log) by Treatment	By treatment.	SAC
3.4.	PK	PK19	Part B: Mean (\pm SD) GSK2831781 Plasma Concentration-Time Plots (Linear and Semi-log) by Treatment	By treatment.	SAC

